17.4 Two-Stage Analysis – Stage 2 Specification

In the 2nd stage of the two-stage approach, a ANCOVA model will be fitted. The pseudo code presented in this section relates to the analysis described in Section 9.3.3 9.3.3 and may need adjustment at the time of analysis.

The dependent variable, Y, will be the slope for each patient which was estimated using simple regression. The covariate is treatment arm (denoted by TRT).

```
proc mixed data = SLOPES1 method=reml alpha=0.05 covtest;
class SUBJID TRT;
model SLOPE = TRT / s ddfm = KR cl;
lsmeans TRT/diff cl;
run;
```

SLOPES1 denotes the slopes of each patient.

Non-inferiority is assessed based on the lower bound of the confidence interval obtained from the LSMEANS statement.

17.5 Two-Stage Analysis with Quantile Regression – Specification

In the 2nd stage of the two-stage approach with quantile regression, a quantiles regression model will be fitted. The pseudo code presented in this section relates to the analysis described in Section 9.2 and may need adjustment at the time of analysis.

The interior point method will be used for estimation of the quantile and resampling will be used for estimation of the SE. The dependent variable, Y, will be the slope for each patient which was estimated using simple regression. The covariate is treatment arm (denoted by TRT).

```
proc quantreg data = SLOPES1 algorithm = interior ci = resampling;
class TRT;
model SLOPE = TRT / quantile = 0.5 seed=1092376;
estimate "PRX-102" intercept 1 TRT 0 1 /cl;
estimate "ADAKSIDASE BETA" intercept 1 TRT 1 0 /cl;
estimate "PRX-102 - ADAKSIDASE BETA" intercept 0 TRT -1 1 /cl;
run;
```

For the sensitivity analysis which includes UPCR, the stratification factor (UPCR < 1; \geq 1 gr/gr; denoted by UPCR STRAT) will be included in the model, as follow.

```
proc quantreg data = SLOPES1 algorithm = interior ci = resampling;
class TRT UPCR_STRAT;
model SLOPE = TRT UPCR_STRAT / quantile = 0.5 seed=1092376;
estimate "PRX-102" intercept 1 TRT 0 1 UPCR_STRAT 0.5 0.5 /cl;
estimate "ADAKSIDASE BETA" intercept 1 TRT 1 0 UPCR_STRAT 0.5 0.5
/cl;
estimate "PRX-102 - ADAKSIDASE BETA" intercept 0 TRT -1 1 /cl;
run;
```

In order to estimate the 25th and 75th percentiles, the "quantile" in the model statement will be changed to 0.25 and 0.75.

The same seed of 1092376 will be used for all the quantile regression models.

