17. APPENDIX A.2 – PRIMARY, SECONDARY, SENSITIVITY AND SUPPORTIVE ANALYSES SPECIFICATIONS

17.1 Random Intercept Random Slope Specifications

The pseudo code presented in this section relates to the analysis described in Section 9.3.29.2, and may need adjustment at the time of analysis. This code to be used in the CSR will be finalized within the programming specifications.

The dependent variable, Y, is eGFR values at different time points (from the baseline visit and onwards, including unscheduled visits). The fixed part of the model includes the following terms: treatment arm (denoted by TRT with 1st level for PRX-102 and 2nd level for AGALSIDASE BETA), time (actual time of measurements in years; denoted by TIMEYR), and treatment arm by time interaction (denoted by TIMEYR*TRT).

```
proc mixed data = DATA1 method=reml alpha=0.05 covtest;
class SUBJID TRT;
model eGFR = TRT TIMEYR TRT * TIMEYR / s ddfm = KR cl;
random INTERCEPT TIMEYR / subject=SUBJID type = UN;
estimate "PRX-102" INTERCEPT 0 TRT 0 TIMEYR 1 TRT*TIMEYR 1 0
/ cl;
estimate "ADALSIDASE BETA" INTERCEPT 0 TRT 0 TIMEYR 1 TRT*TIMEYR 0 1
/ cl;
estimate "EFFECT" INTERCEPT 0 TRT 0 TIMEYR 0 TRT*TIMEYR 1 -1
/ cl;
run;
```

SUBJID denotes the patient ID, DATA1 represent the data to be used for the analysis. Non-inferiority will be assessed based on the lower bound of the confidence interval obtained from the estimate statement labelled as "EFFECT".

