17.2 Random Intercept Model Specifications

The pseudo code presented in this section relates to the analysis described in Section 9.3.4 and may need adjustment at the time of analysis. Variables names are as defined in Section 17.1.

```
proc mixed data = DATA1 method=reml alpha=0.05 covtest empirical;
class SUBJID TRT;
model eGFR = TRT TIMEYR TRT * TIMEYR / s cl;
random INTERCEPT / subject=SUBJID;
estimate "PRX-102" INTERCEPT 0 TRT 0 TIMEYR 1 TRT*TIMEYR 1 0
/ cl;
estimate "AGALSIDASE BETA" INTERCEPT 0 TRT 0 TIMEYR 1 TRT*TIMEYR 0 1
/ cl;
estimate "EFFECT" INTERCEPT 0 TRT 0 TIMEYR 0 TRT*TIMEYR 1 -1
/ cl;
run;
```

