17.3 MMRM Model for Change from Baseline - Specifications

The efficacy analysis is based on a longitudinal mixed model for the change from Baseline in eGFR. The pseudo code presented in this section relates to the analysis described in Section 9.3.59.3.5 and may need adjustment at the time of analysis. In particular, we would confirm the ESTIMATE instructions by LSMEANS.

The dependent variable, Y, will be the change from Baseline in eGFR values at the different visits, denoted below by eGFR_CH. The fixed part of the model will include the following terms: treatment arm (denoted by TRT), visit (denoted by VISIT; class variable based on visits and will include only scheduled visits), and treatment arm by visit interaction (denoted by VISIT*TRT) and eGFR0 to represent the eGFR at Baseline. Only observations at scheduled visits or observations that were mapped to a scheduled visit (See Section 9.1) will be included in the analysis. The pseudo-code presented here was modified compared to the version submitted to FDA in Sep 2020 by adding the Ismeans statement.

```
proc mixed data = DATA1S method=reml alpha=0.05 covtest;
class SUBJID TRT VISIT;
model eGFR_CH = TRT VISIT VISIT * TRT eGFR0 / s ddfm = KR cl;
repeated VISIT / subject=SUBJID type = UN;
lsmeans VISIT * TRT /cl;
estimate "Change from Baseline" TRT 1 -1
VISIT*TRT 0 0 0 0 ... 1, 0, 0, ..0
0 0 0 0 ... -1, 0, 0, ..0 / cl;
run;
```

DATA1S denotes the data, only at scheduled visits, at the interim analysis. The interaction contrast will be set to -1 and 1 for the visit associated with 1 year of treatment (Week 52; Visit 27) and set to -1 and 1 at the visit associated with 2 years of treatment (Week 104; Visit 53).

Non-inferiority is assessed based on the lower bound of the confidence interval obtained from the estimate statement labelled "Change from baseline".

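### SAP section 17 uses two opposite TRT level orders for the primary and supportive contrasts; the 17.7 outcome and the 10.1 interval are also wrong as written

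*SAP*

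**What the plan says.** SAP 9.2 sets the direction in words. The treatment difference is PRX-102 minus agalsidase beta, and non-inferiority needs the lower confidence bound to be at least -3.0 mL/min/1.73 m²/year. It sends the reader to Appendix A.2 (section 17) for the code.

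**PRX-102 first.** 17.1 defines "treatment arm (denoted by TRT with 1st level for PRX-102 and 2nd level for AGALSIDASE BETA" and computes the effect as "estimate 'EFFECT' INTERCEPT 0 TRT 0 TIMEYR 0 TRT*TIMEYR 1 -1". 17.2 takes its variable names from 17.1 and prints "estimate 'PRX-102' INTERCEPT 0 TRT 0 TIMEYR 1 TRT*TIMEYR 1 0". 17.3 prints "estimate 'Change from Baseline' TRT 1 -1", and the 17.7 code has the same 1, -1 pattern.

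**PRX-102 second.** 17.5, the primary model, prints "estimate 'PRX-102' intercept 1 TRT 0 1 /cl" for the PRX-102 arm and "estimate 'PRX-102 - ADAKSIDASE BETA' intercept 0 TRT -1 1 /cl" for the difference. The UPCR sensitivity code in 17.5 uses the same coefficients for TRT.

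**No direction in the code.** 17.4 asks only for an LSMEANS difference; 9.3.3 gives its direction in words. The prose of 17.3 says "The interaction contrast will be set to -1 and 1 for the visit associated with 1 year of treatment", while its code prints 1 and then -1. The 17.7 prose has the same mismatch.

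**Two secondary lines.** The 17.7 text and 10.2 make the change from baseline in log Lyso-Gb3 the outcome, but the 17.7 MODEL statement has `logLysoGb3BL` as both outcome and covariate. 10.1 asks for a Clopper-Pearson interval for a difference in percentages between the arms.

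**The concern.** ESTIMATE coefficients attach to level positions, not to arm names. If 17.5 were run on data ordered as 17.1 declares, the row labelled PRX-102 would show the agalsidase beta median, and the difference would be agalsidase beta minus PRX-102. The non-inferiority rule is one-directional, so the -3.0 bound would then guard against the wrong arm being worse. If the data follow the order implied by 17.5, the primary result is right, and the random-intercept-random-slope (RIRS), random-intercept (RI) and MMRM contrasts are reversed instead.

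The UPCR sensitivity analysis, the 25th and 75th quantiles, the multiple-imputation analysis (17.6) and the subgroup analyses (9.6) all reuse the 17.5 model. They would agree with the primary whether or not it was reversed.

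The two secondary lines do not depend on the level order. Followed literally, neither gives the quantity that the SAP text asks for.

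**Working it through.** **The plan's own figure.** SAP 3.1: difference 1.1, SD 1.5, 44 and 22 completers, two-sided 0.05. SE of a difference in means = 1.5 × √(1/44 + 1/22) = 0.392. Power ≈ Φ(1.1/0.392 − 1.96) = 0.80. The stated 80% is reproduced and is not in dispute.

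**Contrast algebra.** SAP 3.1 gives design slopes of -1.9 for PRX-102 and -3.0 for agalsidase beta.

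| TRT level 1 | 17.5 PRX-102 row (0 1) | 17.5 difference (-1 1) | 17.1 PRX-102 row (1 0) | 17.1 effect (1 -1) |
|---|---|---|---|---|
| PRX-102 (as 17.1 declares) | -3.0 | -1.1 | -1.9 | +1.1 |
| agalsidase beta (as 17.5 implies) | -1.9 | +1.1 | -3.0 | -1.1 |

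Neither row is right throughout. A median regression on one simulated data set showed the same reversal: +1.14 under one order and -1.14 under the other.

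**Size of an undetected primary reversal.** Assume normally distributed slopes, so the SE of a difference in medians = SD × √(π/2) × √(1/n1 + 1/n2). With d the true PRX-102 minus agalsidase beta difference:

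- correct sign: P(pass) = Φ((3 + d)/SE − 1.96)
- reversed sign: P(pass) = Φ((3 − d)/SE − 1.96)

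At SD 1.5 and 52/26 as randomized, SE = 1.5 × 1.253 × 0.240 = 0.452. At d = +1.1:

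- correct: Φ(4.1/0.452 − 1.96), above 0.999
- reversed: Φ(1.9/0.452 − 1.96) = Φ(2.25) = 0.988

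With 44/22 (SE 0.491) the reversed figure is 0.972. At d = 0 the reversal changes nothing.

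Larger effects need other conditions, all at 52/26:

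- SD 3.4 (SE 1.024), d = +1.1: 0.980 correct, 0.459 reversed.
- d = -3.0: 0.025 correct, above 0.999 reversed.

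**The other branch.** Suppose the primary is right and a mean-based supportive row is reversed. The SE for means at 52/26 and SD 1.5 is 0.360. At d = +1.1, P(pass) is above 0.999 with either sign.

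**Would it be seen?** Treat the median and mean differences as bivariate normal with correlation √(2/π) = 0.80, the mean of individual slopes standing in for RIRS. At 52/26 and d = +1.1, conflicting orders put the two estimates on opposite sides of zero in 99% of trials (SD 1.5) or 90% (SD 3.4). With aligned orders that happens in 1% or 10%. At d = 0 the figures are 79% and 21%, so the sign is a weaker signal there.

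**17.7 as printed.** With the same variable on both sides, a least-squares analogue gives a coefficient of 1 on baseline, a treatment effect of 0 and no residual variation. The specified REML fit with an unstructured covariance would have no residual variance to estimate. Either way the model says nothing about change.

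**10.1.** Clopper-Pearson inverts the binomial distribution of one proportion. It does not define an interval for a difference between two independent proportions.

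**The case against.** The SAP calls these blocks pseudo code that may need adjustment, and 17.1 leaves the final code to the programming specifications, where level order would normally be settled. 9.2 and the label in 17.5 both state the intended direction. 17.5 works from its own data set of slopes and does not import the 17.1 definitions. If its levels happened to sort alphabetically by arm name (an assumption), agalsidase beta would come first and 17.5 would be right. All of this stands. It makes the point a conflict to reconcile.

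Three stronger readings are tempting, and the documents do not support them.

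- *The primary contrast is reversed.* The coding of TRT in the data is not given, so this cannot be known.
- *The primary is uniquely unprotected*, because 17.3 says "we would confirm the ESTIMATE instructions by LSMEANS" and 17.5 does not. 17.1 and 17.2 state no such check either. With only an intercept and treatment, the two arm estimates in 17.5 are simply the arm medians and are easy to verify.
- *Only the mean-based rows or the descriptive slopes would reveal a reversal.* The by-arm eGFR plots and the therapeutic-goal tables, which use the same individual slopes, could contradict it too. The dry run uses dummy codes, so it helps only if estimates are compared by arm name.

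The two large figures above are conditional. SD 3.4 is the protocol's tolerance for power, not its expected SD. A true difference of -3.0 sits poorly with the interim declaration of non-inferiority reported in SAP 16.5. On 17.7, text and code disagree, so it looks like a slip. On 10.1, SAP 7.6.2 makes no significance claims for secondary endpoints. Both limit the weight of these lines but do not make them correct.

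**Conclusion.** Wrong as written, of minor to moderate weight, and worth fixing before lock. One TRT coding cannot serve both 17.5 and 17.1 to 17.3. Either the primary family or the RIRS, RI and MMRM contrasts would carry the wrong sign and arm labels relative to 9.2. The documents do not show which, and they do not show that any result would be wrong.

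At the plan's own assumptions an undetected primary reversal costs about one percentage point in the chance of passing at 52/26, and just under three at 44/22. This rests on normal slopes and a large-sample SE for the median. A reader might infer a serious threat to the non-inferiority conclusion. That would need a reversal that nobody notices and, in addition, a far larger SD or a PRX-102 arm that is truly much worse.

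The 17.7 outcome and the 10.1 interval are errors of specification in secondary analyses and do not touch the primary result.

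**What to change.** - State one TRT coding and level order at the head of section 17 and apply it throughout.
- Align to PRX-102 minus agalsidase beta every ESTIMATE line in 17.1 to 17.3, 17.5 and 17.7, the LSMEANS difference in 17.4, and the contrast prose in 17.3 and 17.7.
- Add to 17.5 a check of its two arm medians and their difference, by arm name, against Tables 14.2.1.5.1 and 14.2.1.5.2. Confirm that those tables show the median slope by arm.
- In 17.7, make `logLysoGB3_CH` the dependent variable.
- In 10.1, name a two-sample interval for a difference in proportions, such as Miettinen-Nurminen or Newcombe.

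The cost is a few lines of SAP text before database lock. The cross-check tables and the forest plot are already planned. No new data are needed, and the estimand, margin and sample size do not change.

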17.6 Multiple Imputation for the Primary Analysis

MI under the MAR assumption: missing data for patients who terminated early will be imputed within each treatment arm.

MI includes 3 main steps:

- 1. Imputation: creating N complete datasets. We will use N = 100
- 2. Analysis: analyze each of the N completed data sets
- 3. Pooling: results of the N analyses are combined using Rubin's rule (implemented in SAS using PROC MIANALYZE), in particular a confidence interval for the effect will be provided.

The imputation part (Step 1 above) includes three sub-steps:

- a) For missing eGFR, the time of planned visit will be used. No variation will be incorporated into this.
- b) Create 1 dataset which satisfy monotone missingness. This will be achieved by single imputations of missing eGFR assessments that may have occurred prior to early termination. To achieve that, a simple linear regression will be fitted to the data of each patient (including scheduled and unscheduled visits) and missing eGFR at scheduled time points will be imputed using the prediction from the linear model. Time will be measured relative to day of 1st infusion.

This approach is different than usual approach, that was also in the SAP version submitted to the FDA in Sep 2020 in which monotone missingness is achieved using Markov Chain Monte Carlo (MCMC) approach, within PROC MI with imputations done within each treatment arm. When implementing this approach prior to unblinding using dummy randomization codes, the algorithm did not converge and the reason was the large number of visits that had to be included in the model relative to the sample size. Another approach to rectify this and still using the MCMC was by imputing the missing data in several windows of time to reduce the number of visits at each such time window, however, it involved some arbitrary decisions about choice of windows. Although the approach chosen is based on single imputation, thanks to the large number of planned eGFR assessments, the low number of missing eGFR per patient and the reasonable assumption that they are MAR, it is justifiable to impute missing eGFR from subject's own data instead of borrowing data from other subjects. In case of borderline results (i.e., lower confidence bound very near the non-inferiority and/or superiority limit), additional sensitivity analysis might be performed (e.g., imputing the intermediate missing values via random draws from the distribution as predicted by the per-subject linear regression).

For the interim analysis, most of the patients who had missing data that should be imputed to ensure monotonicity had 1 or 2 missing eGFR assessments. A small number of patients had 3 missing eGFR assessments. One subject that completed the study had 5 missing assessments, and one ongoing subject had 6 missing assessments. This approach will be

discussed, by the blinded team, prior to the final analysis and if there will be concerns about the appropriateness of this approach (e.g., too many missing assessments for a single patient), it will be re-considered.

c) Once the monotone structure is achieved, missing eGFR after early termination will be imputed using the monotone reg command. To reflect the MAR assumption, imputations will be carried out and adjusting to treatment arm. Imputations will be carried out for all patients who terminated early and imputation will be carried out up to Visit 53. The following pseudo-code will be used in this step:

```
proc MI data= OUT_IMP_DATA1 nimpute=100 round= 0.01 seed= 95234761 out = OUT_IMP_MAR_DATA1; class TRT; var TRT eGFR_base eGFR_V3 eGFR_V5 eGFR_V7 eGFR_V9 eGFR_V11 eGFR_V13 eGFR_V14 eGFR_V15 eGFR_V17 eGFR_V19 eGFR_V20 eGFR_V21 eGFR_V23 eGFR_V25 eGFR_V27 eGFR_V29 eGFR_V31 eGFR_V33 eGFR_V35 eGFR_V37 eGFR_V39 eGFR_V40 eGFR_V41 eGFR_V43 eGFR_V45 eGFR_V47 eGFR_V49 eGFR_V51 eGFR_V53; monotone reg eGFR_V3 eGFR_V5 eGFR_V7 eGFR_V9 eGFR_V11 eGFR_V13 eGFR_V14 eGFR_V15 eGFR_V17 eGFR_V19 eGFR_V20 eGFR_V21 eGFR_V23 eGFR_V25 eGFR_V27 eGFR_V29 eGFR_V31 eGFR_V33 eGFR_V35 eGFR_V37 eGFR_V39 eGFR_V40 eGFR_V41 eGFR_V43 eGFR_V45 eGFR_V47 eGFR_V49 eGFR_V51 eGFR_V53; run;
```

In the SAP submitted to the FDA in Sep 2020, the TRT was missing from the var statement. However, in order to impute under MAR, as was planned, the code was modified.

DATA1 represents the data after achieving monotone missingness.

OUT_IMP_MAR_DATA1 will include the 100 complete datasets. Each of the completed datasets will be analyzed using the primary model (two-stage with quantile regression for the median).

```
/* Pooling of the slopes and slopes difference (contrasts from quantile regression model) */
proc MIANALYZE parms = OUT_MAR_ESTIMATES;
by label;
modeleffects estimate;
stderr stderr;
run;
```

OUT_MAR_ESTIMATES represents the contrast estimates using the quantile regression primary model on the 100 complete data set (imputed under MAR).

17.7 MMRM Model for Change from Baseline of log Lyso Gb3

The secondary efficacy endpoint of lyso Gb3 will be analyzed using a longitudinal mixed model for the change from Baseline in log lyso Gb3. The pseudo code presented in this section relates to the analysis described in Section 10.2 and may need adjustment at the time of analysis. In

particular, we would confirm the ESTIMATE instructions by LSMEANS. For the interim analysis, available data beyond one year and up to the cutoff date will be included in the analysis.

The dependent variable, Y, will be the change from Baseline in log lyso Gb3 at the planned visits, denoted below by logLysoGB3_CH. The fixed part of the model will include the following terms: log Lyso Gb3 at Baseline (LogLysoGb3BL) treatment arm (denoted by TRT), visit (denoted by VISIT; class variable based on visits and will include only scheduled visits), and treatment arm by visit interaction (denoted by VISIT*TRT). Only observations at scheduled visits will be included in the analysis.

```
proc mixed data = DATA1S method=reml alpha=0.05 covtest;
class SUBJID TRT VISIT;
model logLysoGb3BL = TRT VISIT VISIT * TRT logLysoGb3BL / s ddfm = KR cl;
repeated VISIT / subject=SUBJID type = UN;
lsmeans VISIT * TRT; estimate "Log Change from Baseline" TRT 1 -1
VISIT*TRT 0 0 0 0 ... 1, 0, 0, ..0
0 0 0 0 ... -1, 0, 0, ..0 / cl;
run;
```

DATA1S denotes the data, only at scheduled visits. For the final analysis, the interaction contrast will be set to -1 and 1 at the visit associated with 2 years of treatment (Week 104; Visit 53).

